6.2.1 Power Calculations

A follow-up rate of study participation at 12 weeks of at least 60% (p_1) would be desirable; a continuation rate below 40% (p_0) would be unacceptable. With 20 eligible and recruited participants alive during a 24 week follow-up period, this study is powered to reject acceptability of these measures if the follow-up rate is less than 40% (10% one-sided type one error) and deemed feasible if the follow-up rate is 64% or more (80% power). If 13 of the 20 patients continue at 12 weeks, we will consider this method to have acceptable adherence for further study (follow-up rate >40%). We will also determine adherence and follow-up rates for both PT and PMR at 24 weeks of follow-up.

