6.0 STATISTICAL ANALYSIS

6.1 Primary Endpoint

In order to evaluate the feasibility of the pilot intervention we will determine, recruitment, adherence, and retention rates at 12-weeks of follow-up. Follow-up will continue through 24 weeks post-enrollment. Recruitment rates will be defined as the proportion of screened older adults accrued relative to those approached in the OSUCCC Thoracic Oncology Clinic.

Successful recruitment rates will be defined as $\geq 50\%$ of older adults (≥ 60 years) approached agree to participate. Study adherence will be defined as the completion of $\geq 70\%$ of the program sessions, repeated assessments, and collection of bio specimens either at the end of the study period or death, whichever occurs first. Retention rates will be defined as the percentage of participants not lost to follow-up at 6, 12, and 24 weeks post-enrollment. Death during active follow-up will not be considered as lost to follow-up. We are excluding those people who die because our population of interest is those who live long enough to benefit from this intervention. We will enroll 30 participants to account for a conservative drop out of 30% for a projected sample size of 20 participants who survive a 6 – month period. Reasons for missing any scheduled collection dates will be documented, and the proportions of missing information at each time point will be calculated.

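### The week-12 rule of 13 out of 20 does not have the stated 10% error and 80% power (exactly 2.1% and 56%), and its denominator is not pinned down

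*Combined protocol and SAP*

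**What the plan says.** Section 6.2.1 calls a week-12 follow-up rate of at least 60% desirable (labelled p1) and one below 40% unacceptable (p0). It then sizes the study: "With 20 eligible and recruited participants alive during a 24 week follow-up period, this study is powered to reject acceptability" of a rate under 40%, at a one-sided type I error of 10%, with the programme "deemed feasible if the follow-up rate is 64% or more (80% power". The decision rule is: "If 13 of the 20 patients continue at 12 weeks, we will consider this method to have acceptable adherence for further study".

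Section 6.1 names as primary endpoint recruitment, "adherence, and retention rates at 12-weeks of follow-up". On deaths it makes three statements:
- Adherence is scored "either at the end of the study period or death, whichever occurs first".
- For retention, "Death during active follow-up will not be considered as lost to follow-up".
- On the population to be studied, the section adds: "We are excluding those people who die because our population of interest is those who live long enough to benefit from this intervention".

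On numbers, 6.1 states "We will enroll 30 participants to account for a conservative drop out of 30% for a projected sample size of 20 participants who survive" six months. Sections 1.1, 1.2, 3.1, 4.1 and 4.14 all speak of 20 participants. Section 1.2 gives the 12-week retention target of 60% with no survival condition.

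**The concern.** A go/no-go rule and its error rates should describe the same test. Here a cut-off of 13/20 (65%) stands next to error rates that look like those of a lower cut-off. If the cut-off is too high, the cost is a false no-go: a workable programme is dropped more often than the plan admits.

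The second issue is who is counted. The rule concerns status at week 12, but its 20 patients are described as alive through week 24, and the sentence in 6.1 excluding those who die is not tied to a time point. A patient who reached week 12 and died in weeks 13 to 24 could be kept or left out. With 20 enrolled in some sections and 30 in another, the plan also does not say what cut-off applies when the number analysed is not 20.

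**Working it through.** **Inputs, all from 6.2.1:** n = 20; go if X ≥ 13; p0 = 0.40; power quoted at 0.64; p1 labelled 0.60; one-sided alpha 0.10.

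**Step 1. Can n = 20 be reproduced?** One-sample normal approximation, with z(0.90) = 1.2816 and z(0.80) = 0.8416:

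n = [1.2816·√(0.40·0.60) + 0.8416·√(0.64·0.36)]² / (0.64 − 0.40)² = 18.5, so 19.

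At n = 20 the same approximation gives power of 82.3%. The sample size therefore fits 40% against 64%. Its critical value is 20 × [0.40 + 1.2816·√(0.24/20)] = 10.8, which means a cut-off of 11, not 13.

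**Step 2. Exact properties at n = 20.** P(go | p) = Σ C(20,x) pˣ (1−p)²⁰⁻ˣ, summed from the cut-off to 20.

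| Go if at least | Alpha at 40% | Power at 60% | Power at 64% |
|---|---|---|---|
| 11/20 | 12.8% | 75.5% | 85.8% |
| 12/20 | 5.7% | 59.6% | 73.2% |
| 13/20 (plan) | 2.1% | 41.6% | 56.4% |
| Stated in 6.2.1 | 10% | not given | 80% |

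The stated pair does not belong to 13/20. Reading the rule as more than 13 moves further away (0.65% and 38.0%). No cut-off at n = 20 keeps alpha at or below 10% and reaches 80% power at 64%: 11 fails on alpha, 12 and 13 fail on power. With 13/20, power reaches 80% only at a true rate of 70.9%.

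A possible origin is 0.64 × 20 = 12.8, rounded up to 13, so that the target rate served as the critical value. That is an inference; the plan does not say so.

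**Step 3. Cost of the mismatch.** False no-go at 64% is 100 − 56.4 = 43.6%, against the implied 20%. At 60% it is 100 − 41.6 = 58.4%.

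**Step 4. Smallest exact cut-off with alpha ≤ 10% at other sizes.**

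| Rule | Observed rate | Alpha at 40% | Power at 60% | Power at 64% |
|---|---|---|---|---|
| 12/21 | 57.1% | 8.5% | 69.1% | 81.2% |
| 14/25 | 56.0% | 7.8% | 73.2% | 85.1% |
| 16/30 | 53.3% | 9.7% | 82.5% | 91.8% |

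The smallest size meeting both limits is 21 for 40% against 64%, and 30 for 40% against 60%. Which alternative is meant therefore matters.

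**Step 5. Denominator, from the text.** The statement on scoring up to death belongs to adherence, and the one on loss to follow-up belongs to retention. The exclusion sentence carries no time point. Section 6.2.1 calls its result adherence, while also using follow-up and continuation for the same rate, so it is not clear which statement governs.

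As an illustration only, with assumed counts: 24 patients are alive at week 12, 13 of them continue (54%), and 4 die in weeks 13 to 24. Dropping those 4 leaves anything from 9/20 (no-go) to 13/20 (go), from identical week-12 data. The documents give no number of late deaths and no continuation rate among them, so the real effect cannot be sized.

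**The case against.** On the cut-off, the best defence is that the rule errs on the safe side: 2.1% is well inside the 10% limit, and a small pilot may choose to be strict. That stands as far as it goes, but the plan states 80% power, and strictness is what takes it to 56%.

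On the denominator the other side is stronger. The phrase about patients alive during 24 weeks is a premise of the sample size. No sentence says that an observed week-12 status is discarded after a later death. Section 6.1 does describe a survivor population and gives a reason, and its references to active follow-up, 24 weeks and six months suggest one common window, though none is attached to the exclusion.

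A reader might go further and infer that the plan conditions the week-12 test on later survival and so inflates the false-go risk above 10%. The documents do not support that. It needs assumed late deaths with poor continuation, and it measures error against everyone alive at week 12, a target the plan did not choose. For a target of 24-week survivors, the survivor rate is not biased. A reader might also infer that 20 patients is the wrong sample size; Step 1 shows that it is roughly right.

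**Conclusion.** The mismatch in 6.2.1 is established from the plan's own figures and needs no assumption beyond independent patients with a common continuation rate. The 13/20 rule has 2.1% type I error and 56% power at 64% (42% at 60%), not 10% and 80%. The harm is an understated risk of a false no-go, about 44% instead of 20% at a true rate of 64%. It should be corrected, since it concerns a decision threshold and is cheap to restate.

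The denominator is a request for clarification. One reading drops patients whose week-12 status was known; the plan neither says this nor rules it out. The difference between 20 and 30 enrolled is a plain inconsistency, and it bears on which cut-off and power apply.

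**What to change.** 1. **Cut-off.** Either keep 13/20 and state alpha 2.1% and power 56% at 64% (42% at 60%), or use 12/20 and state alpha 5.7% and power 73% at 64% (60% at 60%). If the number analysed is not 20, use the smallest exact cut-off with one-sided alpha at or below 10% against 40%, and report its power, as in Step 4. Say whether 60% or 64% is the design alternative.
2. **Deaths.** State that a death after week 12 leaves the patient's observed week-12 status in the analysis. Alternatively, state that 24-week survivors are the target of the 12-week rule, and align 1.2. Fix in advance one rule for deaths before week 12.
3. **Enrolment.** Reconcile 20 (1.1, 1.2, 3.1, 4.1, 4.14) with 30 (6.1).

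**Cost.** No new data are needed. Keeping 13/20 changes only the stated properties. A lower cut-off raises the false-go risk above 2.1%, though within the stated 10%. With the smallest exact cut-off, a go becomes possible at an observed rate below the desirable 60% at some sizes: n = 17 (10/17, 58.8%), n = 19 (11/19, 57.9%) and every n from 21 to 30 (down to 16/30, 53.3%). The plan should disclose this.

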1.2 Hypothesis

We hypothesize that we will be able to accrue 20 older adults (≥ 60 years) with a thoracic malignancy and implement a 12-week virtual health-assisted physical activity + relaxation intervention program with biospecimen collection. We hope to achieve 70% adherence to all sessions and a total patient retention rate of 60% at the end of the 12 – week intervention program.

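### The 13-of-20 retention rule has 56% power at a 64% follow-up rate, not the stated 80%, and 42% at the desirable 60%

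*Combined protocol and SAP*

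**What the plan says.** Section 6.2.1 sets up a single-arm test of 12-week follow-up in 20 participants alive during a 24-week period.

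- Unacceptable rate: "a continuation rate below 40% (p_0) would be unacceptable".
- Desirable rate: "A follow-up rate of study participation at 12 weeks of at least 60% (p_1) would be desirable".
- Error rates and decision count: one-sided type I error of 10%, and the method is "deemed feasible if the follow-up rate is 64% or more (80% power). If 13 of the 20 patients continue at 12 weeks", then "we will consider this method to have acceptable adherence for further study (follow-up rate >40"%).

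The section names no test and does not say what is concluded at 12 of 20. Section 1.2 (Hypothesis) separately hopes for "a total patient retention rate of 60% at the end of the 12"-week programme. Section 6.1 (Primary Endpoint) enrols 30 "for a projected sample size of 20 participants who survive" six months, so 20 is a projection. Section 6.1 also sets thresholds for recruitment (at least 50% of those approached) and adherence (at least 70%), without error rates.

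**The concern.** The power statement and the decision count sit in adjacent sentences and read as one design, but 13 of 20 is 65%, slightly above the 64% at which 80% power is claimed. A cut-off placed next to the expected count is passed only a little more than half the time, so 80% power cannot be right for it. The section also uses two alternatives: 60% is labelled p1, but power is quoted at 64%.

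Feasibility is the primary objective, and this is the only feasibility criterion with stated error rates. A reader told that power is 80% would take a miss as fair evidence against feasibility. The clearest conflict is at 12 of 20. That result equals the 60% called desirable and matches the hoped-for retention in Section 1.2. It also shows a rate above 40% at the plan's own 10% level. Yet it falls short of 13.

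**Working it through.** **Inputs (Section 6.2.1).** n = 20; p0 = 0.40; one-sided α = 0.10; power stated as 80% at 0.64; p1 = 0.60; decision count 13. I read 13 as the minimum for success.

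**Step 1: where the 80% could come from.** Set the count aside and use the normal approximation with null and alternative variances:

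- z = [(0.64 − 0.40) − 1.2816 × √(0.24/20)] / √(0.64 × 0.36/20) = (0.24 − 0.1404) / 0.1073 = 0.928, so power is 82.3%.
- With the null variance only: 0.24/0.1095 − 1.2816 = 0.909, power 81.8%.
- Arcsine: h = 2·asin√0.64 − 2·asin√0.40 = 0.4852; 0.4852 × √20 − 1.2816 = 0.888, power 81.3%.

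The 10%, 80% and 64% figures are therefore roughly a large-sample calculation. Its critical count is 20 × (0.40 + 1.2816 × 0.1095) = 10.8, which means 11 of 20, not 13.

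**Step 2: exact properties of the count.** P(X ≥ k) = Σ_{x=k}^{20} C(20,x) p^x (1−p)^{20−x}.

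| Cut-off | Type I error (p = 0.40) | Power at 0.60 | Power at 0.64 | True rate for 80% power |
|---|---|---|---|---|
| ≥11 | 12.75% | 75.5% | 85.8% | 61.6% |
| ≥12 | 5.65% | 59.6% | 73.2% | 66.3% |
| ≥13 (plan) | 2.10% | 41.6% | 56.4% | 70.9% |
| ≥14 | 0.65% | 25.0% | 38.0% | – |

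No row meets both α ≤ 10% and power ≥ 80% at 0.64. The smallest cut-off within the stated 10% is 12. The plan's 13 is the smallest cut-off that holds a one-sided 5% level.

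**Step 3: what 12 of 20 would show.** The exact one-sided p-value against 40% is 0.057. The one-sided 90% lower confidence limit is 43.3%. So 12 of 20 already supports the conclusion that the plan attaches to 13, a rate above 40%.

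**Step 4: chance of missing the cut-off of 13.**

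- True rate 64%: 1 − 0.564 = 44%, against the 20% implied by 80% power.
- True rate 60%: 1 − 0.416 = 58%.

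**Step 5: other denominators.** Section 6.1 enrols 30 and allows 30% drop-out, which gives 30 × 0.70 = 21, while the plan projects 20. The final number depends on survival. I take 18 to 22 as an illustrative range; it is not in the plan.

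| Rule | Type I error | Power at 0.60 | Power at 0.64 |
|---|---|---|---|
| ≥11 of 18 | 5.8% | 56.3% | 69.7% |
| ≥13 of 18 | 0.6% | 20.9% | 32.2% |
| ≥12 of 21 | 8.5% | 69.1% | 81.2% |
| ≥13 of 22 | 5.5% | 62.4% | 76.2% |

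A fixed count of 13 does not carry over: with 18 evaluable patients it has 32% power at 64%. With 21, the smallest number that works, at least 12 meets both stated targets at 64%. For 80% power at 60%, the smallest number is 30 (≥16; type I error 9.7%, power 82.5%).

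**The case against.** The best defence is that the sentence about 13 states a sufficient condition. It never says that 12 fails or that 13 is the critical value of the 10% test. On that reading the 80% belongs to the large-sample calculation in Step 1 and is acceptable on its own terms. This is fair as to where the 80% comes from, but it does not rescue the plan. Thirteen is the only decision number given, the approximation points to 11, and without 13 there is no stated rule at all. Reading the rule as more than 13 lowers power to 38.0% at 64%.

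A second defence is that this is a small single-arm pilot, feasibility also rests on recruitment and adherence, and a strict bar is a legitimate choice. It is true that the error is conservative: 13 or more of 20 remains sound evidence against 40%, and the decision is affected mainly at exactly 12 of 20. A strict bar is defensible if its properties are reported correctly; here they are not.

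Third, the hoped-for 60% in Section 1.2 may be counted on a different basis from the survivors in Section 6.2.1. That comparison is loose, but Section 6.2.1 gives 60% as its own desirable rate, so the conflict stands without Section 1.2.

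**Conclusion.** The power statement is wrong for the rule the plan adopts. With at least 13 of 20 required and the exact binomial distribution, power at 64% is 56.4% rather than 80%, a shortfall of about 24 percentage points. Power at the desirable 60% is 41.6%. Type I error is 2.1% against a permitted 10%, and that unused allowance is where the power is lost. The arithmetic rests on 20 evaluable patients and on 13 as the minimum for success. It needs nothing from outside the document. The effect is to under-call feasibility, not to over-call it. It must be corrected, because a stated power and a decision threshold for a primary feasibility criterion contradict each other.

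**What to change.** Rewrite Section 6.2.1 in one of two ways, before the 12-week results are known, since choosing between 12 and 13 afterwards would be post hoc.

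1. Set the rule at 12 or more of 20 and state its exact properties: type I error 5.7%; power 60% at 60%, 73% at 64%, and 80% at about 66%.
2. Keep 13 or more of 20 and state its exact properties: type I error 2.1%; power 42% at 60%, 56% at 64%, and 80% at about 71%.

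In either case:

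- say explicitly that a lower count does not meet the criterion;
- use one design alternative in place of 60% and 64%;
- name the exact one-sided binomial test;
- because the number of patients alive through 24 weeks is not fixed, tabulate the cut-off for each plausible denominator. Under the 10% limit, examples are ≥11 of 18, ≥12 of 21 and ≥13 of 22, with the properties shown above. If 13 of 20 is kept, set the cut-offs for other denominators to the same stricter level.

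If the team wants to keep the 10% and 80% at 64% targets, the design number would be 21 evaluable patients with a cut-off of 12. That is what 30 enrolled with 30% drop-out already projects.

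The cost is protocol wording, with no extra patients. On 20 patients the plan must accept a less favourable stated power at 64%: 73% or 56% instead of 80%.

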1.1 Primary Objective

To assess the feasibility of a novel, weekly supervised virtual health-assisted physical therapy plus relaxation intervention delivered to older adults with advanced thoracic malignancy (N=20). The overall goal is to be able to pilot this intervention targeting modifiable risk factors for worsening functional status: physical performance and negative mood.

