4.2 Physical Therapy Intervention

The Physical Therapy Intervention will include a total of 12 weeks with one PT visit per week virtually or in-person depending on in-person clinic limitations due to pandemic or natural disasters. Week 1 assessment will be during an in-person visit with physician team within the OSU Brain and Spine Hospital. The other weekly visits will occur through virtual health monitoring at the best availability of the patient and Physical Therapist. There will be a final visit during week 13 where participants undergo the same assessments as the baseline visit as a routine usual care physical therapy discharge visit. The VH visits will be billed as research or as standard-of-care depending on insurance reimbursement changes for VH visits.

The exercise intervention will begin with a 10 minute warm-up using a portable exercise peddlers either using the patient's feet or arms, depending on their mobility and pain status. For example, if the patient is non-ambulatory and does not have the use of their legs, they will be instructed in peddler use with their arms. The Core exercises will include; seated posterior pelvic tilts and seated without back support seated marches. The resistance training exercises will include shoulder press, tricep extension, bicep curls, upper extremity side raises, chest press, calf raises, marches, standing side leg lifts, leg extension in standing, seated knee extension and clamshells. These will be done in 2 sets of 10 reps using resistance bands appropriate for patient's level of fitness. The cool-down portion will include stretches targeting upper extremities (chest, shoulders, and triceps), lower extremities (calves, quadriceps, and hamstrings) and trunk. Each stretch will be held for 30 seconds each. At week 1 visit patient will receive exercise packet including handouts for above therapeutic exercises three resistance bands (yellow, red and green) in order to progress resistance at home based on patient feedback. The physical therapist will educate and demonstrate appropriate use of the equipment during virtual visits or in-clinic visits depending on encounter type. In order to evaluate how hard the participant is working during the virtual health visits; the relative perceived effort (RPE)¹⁶ will

be used with a target goal of 12-14 on the Borg Rating Scale.¹⁷ This indicates a moderate level of intensity.

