An exercise log in the patient's electronic medical record will be filled out after each workout to keep track of patient progress. The patient will first be prescribed weekly sessions, then it will increase to twice weekly, then three times weekly based on patient behavior and activity tolerance. One session per week will be supervised virtually or in-person by the physical therapist. Additional sessions will be done by the patient on their own per standard-of care physical therapy practice. During the virtual health sessions, the physical therapist will assess barriers to doing their physical therapy and will problem solve with the patients on how to improve adherence. Please see [Appendix B] for a detailed description of the study exercise log.

Physical Therapy Safety Procedures

Upon the initial in-person visit the physician team or physical therapist will perform a standard-of-care safety screening of pulse oximetry assessment, heart rate and blood pressure monitoring, asking if patient has cardiac or pulmonary history. This screening will take into account if the patient is on oxygen, wears glasses or hearing aids. The in-person visit will also determine the location of the VH physical therapy, their emergency contact, and will verify their home address. It will be recommended that the patient perform their physical therapy in the same location each time. The physical therapist will perform a VH safety checklist at the beginning of each session. This checklist may include but not limited to the following questions:

- Where are you currently located?
- Is anyone else home with you?
- Is your cell phone charged and located near you?
- Have you had any new or different chest pain in the last week?
- Have you had any new or different shortness of breath in the last week?

During the VH visits, similar to an in-person visit, if the patient experiences any sudden chest pain or shortness of breath, they will be instructed to stop the activity, sit-down, and call their emergency contact within the home. If they are unable to call for help or are home alone, the physical therapist will call 911 and will notify the treating physician.

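### The 13-of-20 rule in 6.2.1 declares adherence acceptable from a 12-week continuation count; the 70% completion criterion that defines adherence in 6.1 does not enter it

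*Combined protocol and SAP*

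**What the plan says.** The primary objective (1.1) is the feasibility of a "weekly supervised virtual health-assisted physical therapy plus relaxation intervention". Section 6.1 breaks feasibility into three rates: recruitment, adherence and retention.

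- **Adherence (6.1)** requires at least 70% completion "of the program sessions, repeated assessments, and collection of bio specimens either at the end of the study period or death, whichever occurs first".
- **The 6.1 definition of retention:** "Retention rates will be defined as the percentage of participants not lost to follow-up at 6, 12, and 24 weeks post-enrollment".
- **Targets (1.2):** "We hope to achieve 70% adherence to all sessions and a total patient retention rate of 60" per cent. The two measures carry different numbers, and here the 70% is attached to sessions only.
- **Decision rule (6.2.1):** "If 13 of the 20 patients continue at 12 weeks, we will consider this method to have acceptable adherence for further study". The parenthesis that follows explains the result as a follow-up rate above 40%.
- **Next sentence of 6.2.1:** "We will also determine adherence and follow-up rates for both PT and PMR at 24 weeks of follow-up". Adherence and follow-up are again two quantities, with no criterion attached to either.

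**The concern.** Adherence is one of the three components of the primary endpoint, and 13 of 20 is the only rule in the plan that is tied to taking the method forward. The rule's conclusion is about adherence, but what it counts is patients who are still there at week 12. If it is followed as written, a report could state that the pre-specified standard for adherence was met without having compared session, assessment or specimen completion with 70%. No section says how many patients must be adherent, or what adherence result would support a larger trial, so nothing elsewhere in the plan corrects the label.

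**Working it through.** **1. What the rule is built from.** All inputs are in 6.2.1.

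| Input | Value | Described in 6.2.1 as |
|---|---|---|
| p0 | 40% | continuation rate |
| p1 | 60% | follow-up rate at 12 weeks |
| Rate for 80% power | 64% | follow-up rate |
| Cut-off | 13 of 20 | patients who continue at 12 weeks |

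The 60% equals the retention target in 1.2. The 70% appears nowhere in 6.2.1.

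**2. The plan's own figures.** With one-sided 10% error, 80% power and rates of 40% and 64%, the arcsine formula gives h = 2·asin(√0.64) − 2·asin(√0.40) = 0.485 and N = ((1.282 + 0.842)/0.485)² ≈ 19.2, rounded up to 20. The sample size therefore reproduces, and it does so from follow-up rates alone. The 13-of-20 cut-off does not reproduce the stated error rates: exact binomial P(X ≥ 13) is 0.021 at 40% and 0.564 at 64%. That is a separate issue and is not used here.

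**3. Can the rule pass while 70% completion is missed?** The documents do not give completion among patients who continue, so only arithmetic illustrations are possible. They use supervised physical therapy (PT) sessions only. Section 4.2 gives the count: "The Physical Therapy Intervention will include a total of 12 weeks with one PT visit per week" and "One session per week will be supervised virtually or in-person by the physical therapist". That is 12 sessions per patient and 20 × 12 = 240 in all.

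*Study-level reading of 70%.*
- Target: 0.70 × 240 = 168 sessions.
- 13 patients attend all 12: 13 × 12 = 156.
- 7 patients attend one each: 7 × 1 = 7.
- Total: 163/240 = 67.9%, which is 5 sessions short of 168.
- Rule: 13 of 20 continue, so it passes.

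*Per-patient reading of 70%.*
- 0.70 × 12 = 8.4, so at least 9 of 12 sessions are needed.
- A patient who attends 8 of 12, including week 12, has completed 8/12 = 66.7%.
- That patient is participating at week 12 and counts towards the 13, but does not reach 70% of supervised PT sessions.

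**4. What the illustrations do not cover.** The 6.1 criterion also includes assessments and biospecimens, and 1.2 refers to all sessions, which takes in progressive muscle relaxation (PMR). The figures show that the two measures can separate. They do not estimate how far they will.

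**The case against.** The strongest reply is that *continue* means taking part in the program. The opening sentence of 6.2.1 does link the follow-up rate to study participation, and on that reading a patient who has stopped all sessions would not count. This has force, and it rules out a stronger claim that a reader might infer: that the rule passes whatever the session completion, down to all 20 patients attending one session (20/240 = 8.3%) while answering surveys by phone or email. That case needs *continue* to mean only not lost to follow-up, and no section says that answering a survey counts as continuing. The narrower gap remains, because the per-patient illustration above holds on the participation reading.

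Three further objections stand in part.

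- A reader might take 13 of 20 for the only success criterion in the plan. It is not: 6.1 sets at least 50% for recruitment and 1.2 states targets for adherence and retention.
- The study-level illustration is close to the line and covers PT only, so it cannot show that the full 6.1 criterion is missed. The probability of passing 13 of 20 at various continuation rates describes the cut-off and does not measure the mismatch.
- Adherence is defined in 6.1 and reported at 12 and 24 weeks, and a small single-arm pilot does not need a powered rule for each feasibility measure. That is fair, and it limits the fault to the conclusion attached to the rule.

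**Conclusion.** The point holds as an error in the pre-stated conclusion: 6.2.1 tests 12-week continuation and reports the result as adherence, which 6.1 defines differently. This follows from the wording alone and does not depend on how *continue* is read. The reading affects only how far the two measures can diverge. The size of the divergence cannot be estimated from the documents. The 67.9% figure assumes supervised PT only, a study-level 70%, and the stated attendance pattern.

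It would go too far to say that the plan leaves adherence unanalysed or that data are lost. It should be corrected because it concerns a component of the primary endpoint and the only conclusion tied to further study.

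**What to change.** 1. In 6.2.1, change the conclusion of the 13-of-20 rule from adherence to retention (12-week continuation).
2. State whether *continue* means ongoing participation in the program or the 6.1 definition of not being lost to follow-up. The current text points towards the first without settling it, so the sponsor should choose.
3. Base any conclusion about adherence on the 6.1 criterion, reported as the number and proportion of patients who meet it with an exact 95% CI.
4. Confirm that 70% applies per patient. Section 6.1 reads most naturally that way, because it assesses completion at the end of study or at death, but 1.2 is unclear. State also whether the 70% is pooled over sessions, assessments and specimens or applied to each.

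A required number of adherent patients with its own error rates is optional. The cost is wording only, since the session, assessment and sample records are already collected. The downside is that adherence becomes a separate result that may be unfavourable, and it will be imprecise at this size: 12 of 20 adherent patients, for example, has an exact 95% CI of 36% to 81%.
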